2.4.2 Prior, concomitant and post therapies

Prior medications are those medications which were taken and stopped prior to the first dose of study drug in this study.

Concomitant medications are those medications which were taken prior to and continued after the first dose of the study drug or those medication which were given at least once between the day of first dose of study treatment and the date of the last study visit.

All prior and concomitant medications will be summarized for steroid, MTX and NSAIDS table seperately. Medications started and stopped prior to study drug, and then taken again concomitantly will be included in both prior and concomitant summaries separately.

All prior and concomitant medication will be coded using WHO drug dictionary with most updated version. The number and percentage of patients taking concomitant medications prior to start and after start of study drug will presented by ATC class and preferred term. Separate tables showed the frequencies and percentages of patients who took Methotrexate and Oral corticosteroids medications, also by ATC class and preferred term.

All information collected will be listed by patient and visit using safety set.

2.5 Analysis of the primary objective

Not applicable

2.5.1 Primary endpoint

2.5.2 Statistical hypothesis, model, and method of analysis

2.5.3 Handling of missing values/censoring/discontinuations

2.5.4 Supportive analyses

2.6 Analysis of the key secondary objective

Not applicable

2.6.1 Key secondary endpoint

2.6.2 Statistical hypothesis, model, and method of analysis

2.6.3 Handling of missing values/censoring/discontinuations

2.7 Analysis of secondary efficacy objective(s)

Not applicable

2.7.1 Secondary endpoints

2.7.2 Statistical hypothesis, model, and method of analysis

2.7.3 Handling of missing values/censoring/discontinuations

2.8 Safety analyses

Safety measurements include, Extent of exposure and adverse events. All safety endpoints will be summarized for the safety set. All data will be used in safety analyses; however, no imputation will be carried out for missing data.

2.8.1 Adverse events (AEs)

Adverse events starting on or after the time of the first dose of study drug but not later than 7 days (30 days in the case of a SAE) after the date of last dose of study drug taken or those AE present at baseline with increased severity will be classified as a TEAE and will be included in all summaries. AEs which started and ended prior to baseline and AEs which started prior to baseline but whose severity does not change post baseline will not be included in treatment emergent adverse event. In addition, all the treatment emergent AEs will also be listed.

The by-patient listing includes, SOC/PT/Verbatim term, start date, end date, the severity of an AE, Seriousness, whether or not an AE is related to study drug, and whether or not it is a serious AE, action taken with study drug, outcome, duration, discontinue from study. Duration will be calculated as end date – start date +1 and for ongoing last visit date – start date +1.

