1.1 Background

Systemic Juvenile Idiopathic Arthritis (SJIA) is a subset of Juvenile Idiopathic Arthritis (JIA), a serious and potentially disabling form of arthritis that occurs in children 16 years of age and younger, and accounts for approximately 4 - 17 % of JIA (Quartier 2007, Ravelli and Martini 2007). In contrast to other JIA subtypes SJIA is associated with systemic symptoms such as fever, rash, anemia, leukocytosis, elevated erythrocyte sedimentation rate and acute-phase. The peak age of disease onset lies between 18 months and 2 years, but SJIA may occur in children of any age and, rarely, in young adults too (Woo 2006).

Several lines of evidence show that interleukin-1 (IL-1) plays a pivotal role in the pathogenesis of SJIA (Dinarello 2005, Pascual et al 2005).

Ilaris[®] (Canakinumab) is a human monoclonal anti-human interleukin-1 beta (IL-1 beta) antibody of the IgG1/ κ isotype. Canakinumab binds with high affinity specifically to human IL-1 beta and neutralizes the biological activity of human IL-1 beta by blocking its interaction with IL-1 receptors, thereby preventing IL-1 beta-induced gene activation and the production of inflammatory mediators. Canakinumab has a half-life of approximately 21-28 days.

To date, four clinical studies (CACZ885A2203, CACZ885G2305, CACZ885G2301, and CACZ885G2301E1) have been performed by Novartis to evaluate canakinumab as a treatment for patients with SJIA.

Ilaris[®] received Marketing Authorization by the EMA for patients with Systemic Juvenile Idiopathic Arthritis (SJIA) on August 2013 for *the treatment of active Systemic Juvenile Idiopathic Arthritis (SJIA) in patients aged 2 years and older who have responded inadequately to previous therapy with non-steroidal anti-inflammatory drugs (NSAIDs) and systemic corticosteroids. Ilaris[®] can be given as monotherapy or in combination with methotrexate.*

Study CACZ885G2301E1 is a Phase III study designed to assess long-term safety and efficacy data for patients with SJIA who either participated in the CACZ885G2305 and CACZ885G2301 registration studies or were treatment-naïve to canakinumab. In France, 48 patients were enrolled in the CACZ885G2301E1 study at four centers (Necker, Kremlin- Bicêtre, Lyon, and Strasbourg). Study CACZ885G2301E1 is ending on November 2014 and 3 sites (Necker, Kremlin-Bicêtre, and Lyon) still have patients under treatment.

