In case of use of oral contraception women should have been stable on the same pill for a minimum of 3 months before taking study treatment.

Reliable contraception should be maintained throughout the study and until 3 months after canakinumab discontinuation.

5 Treatment

Initial canakinumab dose:

For patients previously included in study CACZ885G2301E1 (SJIA)

Patients will continue the same dose as their last dose administered in the study CACZ885G2301E1: canakinumab 4mg/kg (or 300mg max) or 2mg/kg (150mg max) every 4 weeks.

Canakinumab dose reduction from 4 mg/kg to 2 mg/kg every 4 weeks in steroid-free patients with prolonged strong response was permitted in the ongoing extension study CACZ885G2301E1 at the request of the treating physician and with the agreement of Novartis.

Similarly, in this study, the canakinumab dose may be reduced from 4mg/kg (300 mg max) to 2mg/kg (150 mg max) every 4 weeks and then interrupted after a prolonged remission according to the investigators judgment.

For patients previously included in study CACZ885N2301 (Periodic Fever syndromes indications: TRAPS, HIDS or crFMF)

Patients will continue one of the following regimens as received at the end of the study:

- canakinumab 150 mg (or 2 mg/kg for patients weighing ≤ 40 kg) q4w
- canakinumab 150 mg (or 2 mg/kg for patients weighing ≤ 40 kg) q8w
- canakinumab 300 mg (or 4 mg/kg for patients weighing ≤ 40 kg) q4w
- canakinumab 300 mg (or 4 mg/kg for patients weighing ≤ 40 kg) q8w

In case of re-flare (according to investigators judgment), patients will be allowed to increase the dose as follow:

- If patients receive canakinumab 150 mg q8w, the dose of canakinumab will be increased to 150 mg q4w
- If patients receive canakinumab 150 mg q4w, the dose of canakinumab will be increased to 300 mg q4w
- If patients receive canakinumab 300 mg q8w, the dose of canakinumab will be increased to 300 mg q4w

For patients previously included in study CACZ885G2306 (SJIA):

The patients will continue the same dose as their last dose administered at the end of the tapering period study CACZ885G2306.

Then, patients will continue one of the following regimens:

- Canakinumab 4mg/kg q4wks
- Canakinumab 2mg/kg q4wks
- Canakinumab 1mg/kg q4wks
- Canakinumab 4mg/kg q8wks
- Canakinumab 4mg/kg q12wks

The patients who have withdrawn canakinumab per protocol may resume canakinumab after a relapse at a starting dose of 4 mg/kg (maximum 300 mg) every 4 weeks.

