Dose adjustments (for all patients):

Patients may receive an up-titration or may resume canakinumab if they re-flare (maximum dose of 300 mg (or 4 mg/kg s.c for patients ≤ 40 kg q4w).

The canakinumab dose interval (i.e. every 6, 8 or 12 weeks) may also be prolonged in patients with adequate response according to investigators judgment.

Every patient withdrawn from CACZ885GFR01 study due to a remission will be allowed to resume canakinumab in case of relapse and will be followed up again in the study.

Canakinumab will be administered at the study center.

End of treatment

For patients treated for SJIA:

Investigators will be informed as soon as this indication is commercially available in order to organize at the next planned visit the dropout of the patients. If no visit is planned within 2 months of notification reception, the investigators will have to contact the patient in order to organize patient's study termination. Investigators will have the possibility to perform a last canakinumab administration during the last visit of the protocol.

For patients treated for TRAPS, HIDS and crFMF:

Investigators will be informed as soon as this indication is commercially available in order to organize at the next planned visit the dropout of the patients. If no visit is planned within 2 months of notification reception, the investigators will have to contact the patient in order to organize patient's study termination. Investigators will have the possibility to perform a last canakinumab administration during the last visit of the protocol.

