2.1.1 General definitions

Study treatment: refers to: Ilaris = ACZ885

Study treatment start and end date: Study treatment start date is defined as the first date of study drug is administered and recorded on the Study Medication Dosing Record in CRF page. Similarly, study drug end date is defined as the last date of study drug is administered.

Study day: Study day will be calculated as (event date – study drug start date + 1 day) for events that occurred on or after study drug start date (e.g. visit, adverse events). For events prior to study drug start date (e.g., time of diagnosis), study day will be negative and calculated as (event date – study drug start date).

Baseline and post baseline: In general, a *baseline* value refers to the last measurement made prior to administration of the first dose of study treatment or the average values taken prior to administration of the first dose of study treatment. A post-baseline value refers to a measurement taken after the first dose of study treatment.

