2.4 Treatments (study treatment, rescue medication, concomitant therapies, compliance)

2.4.1 Study treatment / compliance

The maximal total single dose of canakinumab (ACZ885) allowed is 300 mg, which is administered as two subcutaneous 150 mg injections once every 4 weeks.

The canakinumab dose interval (i.e. every 6, 8 or 12 weeks) may also be prolonged in patients with adequate response according to the clinical response and investigators judgment.

The extent of exposure will be examined to determine the degree to which safety can be assessed for canakinumab (ACZ885). The extent of exposure to study drug will be characterized according to the duration of exposure and the number of patients exposed.

Duration of exposure to the treatment will be calculated as the number of days between the first dose date and the last dose date exposed to that treatment over the specified period in Ilaris (ACZ885GRR01) study, expressed as: Duration of exposure = ((Date of last known dose of study drug – Date of first dose of study drug) – Number of days interrupted) + 1.

The duration of exposure (in days) and the cumulative volume administered (in mL) will be summarized with descriptive statistics (n, mean, median, standard deviation, minimum, maximum, Q1, Q3) for the safety set.

The total number of doses (injections) administered, number of 2 mg/kg doses administered, number of 4 mg/kg doses administered will be summarized with number and percentage for overall, 2mg/kg and 4 mg/kg dose group for safety set. By subject listing along with dose date will be provided for safety set.

The duration of exposure (in days) and number of injection will be summarized for the safety set as

- a continuous variable with the standard descriptive statistics
- a categorical variable for number of does (injections) administered classified into 1-4, 5-8, 9-12, 13-16, 17-20, 21-24 with number and percentage for below group.
 - Number of doses (injections) administered
 - Number of 1 mg/kg q4w doses administered
 - Number of 2 mg/kg q4w doses administered
 - Number of 4 mg/kg q4w doses administered
 - Number of 2 mg/kg q8w doses administered
 - Number of 4 mg/kg q12w doses administered
 - Other dose administered
 - No dose administered
- Number of subject and percentage at baseline, reduction in dose at end of study, increase in dose at end of study and stable dose with all dose amount.

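### With one first-to-last-dose window per patient, a new adverse event in an off-drug remission gap is treatment-emergent if the patient later restarts canakinumab, but not otherwise

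*SAP*

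**What the plan says.** **The adverse event window.** SAP 2.8.1 classifies as treatment-emergent "Adverse events starting on or after the time of the first dose of study drug but not later than 7 days" after the last dose, with "30 days in the case of a SAE) after the date of last dose of study drug taken" for serious events. A second limb adds, with no time limit, "or those AE present at baseline with increased severity will be classified as a TEAE". SAP 2.1.1 gives each patient one start date, the first administration. For the end, "study drug end date is defined as the last date of study drug is administered". No SAP section defines treatment courses, re-entry or off-drug time for adverse events.

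**Stopping and restarting.** Under protocol section 5, patients from CACZ885G2301E1 may have the dose reduced and "then interrupted after a prolonged remission according to the investigators judgment". Under dose adjustments for all patients, the same section states: "Every patient withdrawn from CACZ885GFR01 study due to a remission will be allowed to resume canakinumab in case of relapse", with follow-up again in the study. Section 5.5.5 permits interruptions on investigator judgment for anyone. Section 5.5.1 keeps the parent-study identifier, and no new number at restart is described. No maximum gap is stated.

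**Exposure.** SAP 2.4.1 takes last dose date minus first dose date and then subtracts "Number of days interrupted) + 1". It does not say what counts as an interruption.

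**The concern.** Safety is the only data objective of this study, and the treatment-emergent tables are its main product. A definition of treatment-emergent should depend on what had happened to the patient when the event began. Here the final administration closes the window, so a later restart reaches back and changes the status of events that began off drug. By protocol section 5, restart after a remission stop follows relapse, so the reclassification is tied to disease course: relapsers contribute their off-drug events, and patients who stay in remission do not.

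The tables exposed are those for all treatment-emergent events, infections, maximum severity, suspected relationship, and permanent discontinuation. SAP 2.8.1 also commits only to listing treatment-emergent events, so the same off-drug event is listed for a restarter and missing from that listing for a non-restarter.

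**Working it through.** There is no sample size or power figure to reproduce; the study is descriptive. The check applies the SAP rule to two patients who differ only in whether they restart.

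**Inputs.** From SAP 2.8.1 and 2.1.1: window = first dose to final dose + 7 days (AE) or + 30 days (SAE). Assumed, because the documents give no dates: 13 doses every 4 weeks from day 1, a stop for remission and, in one patient, a restart 240 days later with 6 further doses every 4 weeks.

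**Windows.**
- Last dose before the stop: 1 + 12 × 28 = day 337.
- Never restarts: window closes on day 337 + 7 = 344 (AE) or 337 + 30 = 367 (SAE).
- Restarts: first new dose on day 337 + 240 = 577; final dose on day 577 + 5 × 28 = 717; window closes on day 724 (AE) or 747 (SAE).

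**Is a new-onset event treatment-emergent?**

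| Onset after day 337 | SAP rule, never restarts | SAP rule, restarts | 7/30-day tail per course, both patients |
|---|---|---|---|
| +5 days, AE or SAE | yes | yes | yes |
| +20 days, AE | no | yes | no |
| +20 days, SAE | yes | yes | yes |
| +60, +91 or +150 days, AE or SAE | no | yes | no |

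Restarting at 180 or 365 days gives the same pattern.

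**Drug remaining.** Protocol 1.1: "Canakinumab has a half-life of approximately 21-28 days". After 24 weeks (168 days) off drug, 0.5^(168/21) = 0.4% to 0.5^(168/28) = 1.6% remains, yet an event then is treatment-emergent if dosing later resumes.

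**Exposure in the restarter.** First to last dose is 717 − 1 + 1 = 717 days. Subtracting the whole gap leaves 717 − 240 = 477. Subtracting only the part beyond one 28-day interval leaves 717 − 212 = 505. The adverse event window still covers all 717 days plus the tail.

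**Can the wording be read another way?** Suppose *last dose* meant the most recent dose before the event. Days more than 7 after a dose would then fall outside the window during ongoing treatment: 28 − 8 = 20 of 28 days (every 4 weeks), 34 of 42 (6 weeks), 48 of 56 (8 weeks) and 76 of 84 (12 weeks). That is unworkable and contradicts SAP 2.1.1.

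**Size.** The synopsis allows up to 40 patients (section 4 says 41). One patient with a gap event and no other treatment-emergent event moves the any-event percentage by 1/40 = 2.5 points. If 10 of 40 patients (assumed) had such an event, they would add 0%, 12.5% or 25% when 0, 5 or all 10 restart.

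**The case against.** Much of the case on the other side stands and limits the point.

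- **Deaths.** A reader might infer that the death summary in SAP 2.8.2 is inflated in the same way. It cannot be: a patient who dies off drug does not restart, so the last dose before death is the final dose under either rule.
- **SAE table.** A reader might infer that it is distorted too. SAP 2.8.1.1 does not limit that table to treatment-emergent events, and SAP 2.8 says all data are used, although 2.8.1 ties the definition to all summaries. The effect there is uncertain.
- **Capture.** Not every gap event reaches the database. After formal withdrawal, protocol 7.1 sends later non-serious events to source documents, and 7.2.2 requires SAEs after 30 days only if causality is suspected. Patients interrupted but still in the study have the control visit at Week 13 ± 7 days (section 6).
- **Relapse.** It is tempting to say that every restarter brings an off-drug relapse into the tables. Section 5.5.5 allows interruptions for other reasons, and a relapse counts only if recorded as an adverse event.
- **Worsened baseline events.** These are treatment-emergent under the second limb whether or not the patient restarts.
- **Exposure mismatch.** The planned tables give patients and percentages, counted once per term, with no exposure-adjusted rates. No planned rate is wrong.
- **Direction of error.** The present rule errs towards inclusion. A 7-day tail puts a day-8 event off treatment while 0.5^(8/21) = 77% to 0.5^(8/28) = 82% of drug remains.
- **Protocol version.** The SAP cites protocol version 04 and the resume rule appears under Amendment 5. A reader might infer that the SAP predates the rule, but the documents do not map version numbers to amendment numbers.

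None of this removes the dependence on a later restart for recorded, new-onset events in the treatment-emergent tables and listing.

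**Conclusion.** The point holds in this form: for a recorded, new-onset adverse event more than 7 days (30 for an SAE) after the dose preceding an off-drug gap, treatment-emergent status depends on whether the patient later restarts. It follows from the SAP's stated definitions, and the protocol foresees the situation. It affects the treatment-emergent tables and listing. The SAP also treats the same days as unexposed in one section and inside the adverse event window in another.

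The size cannot be fixed from the documents, which give no number of stops, restarts or gap lengths. It is zero if nobody restarts or no gap event is recorded; otherwise it is 2.5 points per affected patient in the any-event row, assuming a safety set of 40 and no other treatment-emergent event in that patient. This is an inexpensive improvement worth making before database lock. It does not show that the study's safety conclusions would be wrong.

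**What to change.** In SAP 2.8.1, apply the existing 7- and 30-day tails to each treatment course.

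1. For analysis only, end a course at the last dose before a recorded interruption or withdrawal for remission, or before any dosing gap longer than a prespecified length tied to the protocol's own schedule (for example, no dose by the Week 13 control visit). A new course starts at the first dose on resumption. Because section 6 also allows intervals longer than 12 weeks, state how such patients are handled.
2. Use the same definition for interrupted days in SAP 2.4.1.
3. Show events outside all courses in a separate off-treatment column, for restarters and non-restarters alike.
4. List all adverse events, not only treatment-emergent ones.
5. State whether the SAE table is limited to treatment-emergent events. Leave SAP 2.8.2 unchanged.

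The cost is SAP wording, one flag derived from dosing dates and interruption or withdrawal records, and one extra column. Slightly fewer events will appear as treatment-emergent. Given the half-life, the off-treatment column must stand beside the treatment-emergent column so that events soon after the tail are not lost. Some dependence on later dosing remains: an event on day 50 after a dose is on treatment if the next dose comes on day 84 and off treatment if the patient stops. The gap limit bounds this, whereas the present rule sets no bound.

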9.4 Analysis of variables

9.4.1 Variables

a. Efficacy variables

There is no efficacy assessment in this study

b. Safety variables

Adverse events will be coded using the MedDRA dictionary that provides the primary system organ class and preferred term information. Adverse events will be presented in two parts:

- Adverse events (including infections)
- Infectious adverse events

Adverse events will be summarized for each disease by presenting the number and percentage of patients having any adverse event, having any adverse event in each primary system organ class and having each individual adverse event based on the preferred term. All other information collected (e.g. severity, relationship to study drug, or microorganism for infectious adverse events) will be tabulated and listed as appropriate.

Deaths, serious adverse events, and adverse events leading to discontinuation of study drug will be summarized by primary system organ class and preferred term and listed.

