2.12	Biomarkers.....	14
2.13	Other Exploratory analyses.....	14
2.14	Interim analysis.....	14
3	Sample size calculation	14
4	Change to protocol specified analyses	14
5	Appendix	14
5.1	Imputation rules	14
5.1.1	Study drug	14
5.1.2	AE date imputation	14
5.1.3	Concomitant medication date imputation	16
5.2	AEs coding/grading	17
5.3	Laboratory parameters derivations	18
5.4	Statistical models	18
5.5	Rule of exclusion criteria of analysis sets.....	18
6	Reference.....	18

List of abbreviations

AE	Adverse event
TEAE	Treatment emergent adverse event
CRF	Case Report/Record Form
CPO	Country Pharma Organization
CRO	Contract Research Organization
CSR	Clinical Study Report
DS&E	Drug Safety and Epidemiology
ICH	International Conference on Harmonization
IEC	Independent Ethics Committee
MedDRA	Medical Dictionary for Drug Regulatory Affairs
MTX	Methotrexate
NSAID	Non-steroidal anti-inflammatory drug
RAP	Report and Analysis Process
SAE	Serious adverse event
SAP	Statistical Analysis Plan

Introduction

This document contains details of the statistical methods which will be used in the phase IV clinical trial CACZ885GFR01. This is an extension study to collect additional safety data (serious and non-serious adverse events) and to provide continuous Ilaris® (canakinumab) to patients in France who completed study CACZ885G2301E1, CACZ885N2301 or CACZ885G2306 until canakinumab (Ilaris®) is commercially available and reimbursed in France for these indications.

Data will be analyzed by Novartis and/or by the designated CRO and *statistical software SAS* version 9.4 according to the data analysis section 9 of the study protocol version 04 which is available in Appendix 16.1.1 of the CSR. Important information is given in the following sections and details are provided, as applicable, in Appendix 16.1.9 of the CSR.

Unless otherwise specified, the statistical methodologies including the analysis sets, analysis models, algorithms and conventions are following then interventional study protocol ACZ885GFR01.

The planned analysis is described in Section 9 of the protocol (Appendix 16.1.1 of CSR).

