2.8.1.1 Adverse events of special interest / grouping of AEs

AEs by primary system organ class and preferred term

The number and percentage of patients who reported treatment emergent adverse events will be summarized for each primary system organ class and preferred term. Primary system organ classes will be sorted alphabetically and, within each primary system organ class, the preferred terms will be sorted in descending order of frequency.

If a patient reported more than one adverse event with the same preferred term, the adverse event will be counted only once at the preferred term level. If a patient reported more than one adverse event within the same primary system organ class, the patient will be counted only once at the system organ class level.

Treatment emergent adverse events will be presented in two parts:

- Adverse events (including infections)
- Infectious adverse events

AEs by severity

All treatment emergent adverse events will be summarized by maximum severity for each primary system organ class and preferred term. If a patient reports more than one adverse event within the same primary system organ class, only one adverse event will be counted for that patient at the highest severity level in the total row for each primary system organ class. If a patient reported more than one adverse event with the same preferred term, the highest (maximum) severity will be presented.

AEs suspected to be related to study drug

The treatment emergent adverse events suspected to be related to the study drug (according to the investigators) will be summarized by primary system organ class and preferred term. Relationship to study drug is considered as suspected for those events where "Relationship to study drug" is answered by the investigator as "Suspected".

AEs leading to permanent study drug discontinuation

Treatment emergent adverse events leading to permanent study drug discontinuation will be summarized by primary system organ class and preferred term.

Serious Adverse Event (SAE)

Number and percentage of patients with serious adverse events, regardless of study drug relationship, will be presented by primary system organ class and preferred term.

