2.14 Interim analysis

Not applicable

3 Sample size calculation

No sample size calculation was performed for this extension study which will include all eligible subjects who complete CACZ885G2301E1 or CACZ885N2301 study and meet the eligibility criteria.

4 Change to protocol specified analyses

Not applicable

5 Appendix

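### The SAP's table of AEs leading to discontinuation drops a new non-serious AE that starts more than 7 days after an injection, because the patient stopped

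*SAP*

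**What the plan says.** SAP 2.8.1 gives two routes into the treatment-emergent (TEAE) set. A new AE must start on or after the first dose "but not later than 7 days (30 days in the case of a SAE) after the date of last dose of study drug taken". The other route is for pre-existing events: "or those AE present at baseline with increased severity will be classified as a TEAE". A new AE cannot use the second route.

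SAP 2.1.1 ties the end of treatment to an injection date, not to the end of a dosing interval: "study drug end date is defined as the last date of study drug is administered". Protocol section 6 and SAP 1.2 put injections and visits 4, 6, 8 or 12 weeks apart.

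SAP 2.8.1.1 restricts the table at issue: "Treatment emergent adverse events leading to permanent study drug discontinuation will be summarized by primary system organ class and preferred term". The listing named in SAP 2.8.1 is also of TEAEs: "In addition, all the treatment emergent AEs will also be listed".

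Protocol 9.4.1 asks for the same output without a time limit: "adverse events leading to discontinuation of study drug will be summarized by primary system organ class and preferred term and listed". The SAP introduction defers to the protocol ("The planned analysis is described in Section 9 of the protocol"), and SAP section 4, "Change to protocol specified analyses", is marked as not applicable.

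**The concern.** The window is anchored on the last dose, and the last dose is itself decided by whether the patient stops. Take a new non-serious AE that starts two weeks after an injection. If the patient continues, the next injection moves the last dose forward and the AE is counted. If the AE makes the patient stop, the earlier injection stays the last one, the AE falls outside the 7 days, and it is not counted. The rule therefore works against the one table meant to show events that ended treatment.

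Collecting safety data is the study's only scientific objective, and this is one of the few safety outputs that the protocol names. A reader could see a patient in the disposition table as stopped for an AE and find no matching row by system organ class and preferred term. The overall, severity and drug-related tables are also limited to TEAEs, so the event would be missing there too.

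**Working it through.** The plan states no figure for this point, so there is none to reproduce. The check applies the SAP rule to each possible onset day.

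**Inputs**
- Window for a new AE: last dose + 7 days, or + 30 days if serious (SAP 2.8.1).
- Last dose: date of the last injection (SAP 2.1.1).
- Interval I: 28, 42, 56 or 84 days (Protocol section 6; SAP 1.2).
- Visit window: ±7 days (Protocol section 6, visit table).
- Half-life: 21 to 28 days (Protocol 1.1).

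**Step 1. The patient stops, so the injection before onset is the last dose.** Onset days run from 0 (injection day) to I − 1. Non-serious AEs are kept on days 0–7, which is 8 days, so the excluded share is (I − 8)/I. SAEs are kept on days 0–30, which is 31 days, so the excluded share in this table is max(0, I − 31)/I.

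| Interval | Non-serious excluded | SAE excluded |
|---|---|---|
| 4 weeks | 20/28 = 71.4% | 0/28 = 0% |
| 6 weeks | 34/42 = 81.0% | 11/42 = 26.2% |
| 8 weeks | 48/56 = 85.7% | 25/56 = 44.6% |
| 12 weeks | 76/84 = 90.5% | 53/84 = 63.1% |

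**Step 2. Same AE, same onset day, but the next injection is given.** The last dose is then at day I or later, so every onset day from 0 to I − 1 precedes it. Excluded: 0 days at every interval. The stop alone makes the difference.

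**Step 3. Visit window.** For non-serious AEs, a 4-week interval of 21 to 35 days gives 13/21 = 61.9% to 27/35 = 77.1%. A 12-week interval of 77 to 91 days gives 69/77 = 89.6% to 83/91 = 91.2%.

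**Step 4. Sensitivity to uniform onset.** Shares of days equal shares of events only if onset is uniform over the interval. Suppose instead that onset follows drug level with first-order decline (an assumption; absorption is ignored). With r = 0.5^(1/h), the excluded share is (r^8 − r^I)/(1 − r^I). For h = 21 and h = 28 this gives:
- 4 weeks: 61.5% and 64.1%
- 6 weeks: 69.1% and 72.2%
- 8 weeks: 72.5% and 76.0%
- 12 weeks: 75.2% and 79.5%

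Under the same decline, the fraction of drug left on day 8, the first excluded day, is 0.5^(8/21) = 76.8% to 0.5^(8/28) = 82.0%.

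**Step 5. What is not affected.** Baseline AEs that worsen enter by their own clause. All deaths are listed (SAP 2.8.2). The SAE table is not worded as TEAE-only. A patient dosed at the last visit, or who resumes after a gap, has a later last dose that brings the earlier event back in.

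**The case against.** The strongest reply is that little is shown to be lost. The study takes about 40 patients who, by Protocol 3.5, have responded to the drug for at least 2 years. The gap needs a new, non-serious AE that starts after day 7, forces a permanent stop and is followed by no further injection. No AE rate in the documents shows that even one such event will occur, and the analysis is descriptive, so no test or estimate changes. This stands, and it limits the size of the point.

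The missing listing is also less certain than the missing table. SAP 2.8.1 does not say that only TEAEs are listed, SAP 2.8 says in general terms that all data are used, and the SAP follows the protocol unless it specifies otherwise. The protocol's listing of discontinuation AEs may therefore still be produced, and disposition outputs give the primary reason for stopping. This stands in part. None of it restores the table, where the SAP does specify otherwise, and disposition carries no system organ class or preferred term.

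A stopping SAE after day 30 still appears in the SAE table, so the SAE percentages describe absence from one table, not loss of the event. That is right.

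Finally, a TEAE cut-off is normal practice, and it can be argued that defining one is operational detail and need not be declared in section 4. The cut-off is acceptable for the general AE tables. The fault is applying it to a table whose membership should follow the action recorded for the event.

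**Conclusion.** The concern holds as the SAP is written. A new non-serious AE that starts after day 7 of the final interval and ends treatment is excluded from the table of AEs leading to discontinuation, while the same AE in a patient who is dosed again is included. The excluded part of the final interval runs from 71% of days at 4-week dosing to 90% at 12-week dosing. For stopping SAEs in this table it is 0% at 4 weeks, rising to 63% at 12 weeks.

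The mechanism needs no assumption beyond the SAP's own definitions. Reading the day shares as event shares does assume uniform onset; under the drug-level alternative the non-serious shares are about 62% to 79%. The number of events affected across the study cannot be derived and is probably small. The point should be fixed because the table is a protocol-specified safety output, the restriction departs from Protocol 9.4.1 without being declared, and the repair is cheap.

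**What to change.** - **SAP 2.8.1.1:** tabulate and list, by system organ class and preferred term, every AE whose action taken is permanent discontinuation if it is now a TEAE or starts on or after the first dose, with no post-dose cut-off.
- **SAP 2.8.1:** list all recorded AEs, adding days since last dose and a TEAE flag.
- **TEAE definition:** it can stay for the other tables. If it is widened, run it to the later of the last study visit and the existing limit (last dose + 7 days, or + 30 days for SAEs), so that no event now counted is lost. Extending the non-serious limit to 30 days would close the gap only at 4-week dosing; the SAE column above shows what would remain.
- **SAP section 4:** declare any cut-off that is kept for this table, with its reason.

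The cost is one sentence, one wider listing and one flag. Protocol 7.1 already records permanent discontinuation for each AE, and the by-patient listing already carries action taken, so no new data are needed.

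There are two drawbacks. Counts in one table may rise slightly, with some events long after dosing. If the TEAE definition stays as it is, the discontinuation table will also no longer be a strict subset of the overall AE table. A footnote, the flag and days since last dose let a reader reconcile the two.
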